19.0 Confidentiality

A. Confidentiality of Study Data

Describe the local procedures for maintenance of confidentiality of study data and any records that will be reviewed for data collection.

19.1 A. Where and how will all data and records be stored? Include information about: password protection, encryption, physical controls, authorization of access, and separation of identifiers and data, as applicable. Include physical (e.g. paper) and electronic files.

Response:

Hard copies of raw data collected during the study will be stored in a locked file cabinet in the Division of Behavior Medicine. Only study staff associated with the project will have access to the data and all computer files containing identifiable data will be password protected and only the PI and members of the research staff will have access to the data. Participant identities will be coded and will not be associated with any published results. Electronic files will be stored on the secure shared drive of the Division of Behavioral Medicine, which is assessable with a password that is only known by study personnel.

19.2 A. How long will the data be stored?

Response:

Identifiable data will be stored for at least 3 years following study completion. De-identified data will be retained indefinitely.

19.3 A. Who will have access to the data?

Response:

Only study staff working on the project will have access to the data.

19.4 A. Who is responsible for receipt or transmission of the data?

Response:

The Principle Investigator and Co-Investigators will be responsible for the receipt or transmission of data.

19.5 A. How will the data be transported?

Response:

Data will not be transported locally; the data will remain at the local site.

B. Confidentiality of Study Specimens

Describe the local procedures for maintenance of confidentiality of study specimens.

- N/A: No specimens will be collected or analyzed in this research.
(Skip to Section 19.0)

19.6 B. Where and how will all specimens be stored? Include information about: physical controls, authorization of access, and labeling of specimens, as applicable.

Response:

19.7 B. How long will the specimens be stored?

Response:

19.8 B. Who will have access to the specimens?

Response:

19.9 B. Who is responsible for receipt or transmission of the specimens?

Response:

19.10 B. How will the specimens be transported?

Response:

20.0 Provisions to Monitor the Data to Ensure the Safety of Subjects

- N/A: This study is not enrolling subjects, or is limited to records review procedures only. This section does not apply.

NOTE: Minimal risk studies may be required to monitor subject safety if the research procedures include procedures that present unique risks to subjects that require monitoring. Some examples include: exercising to exertion, or instruments that elicit

suicidality or substance abuse behavior. In such cases, N/A is not an acceptable response.

20.1 Describe the plan to periodically evaluate the data collected regarding both harms and benefits to determine whether subjects remain safe.

Response:

Data will be reviewed weekly and secured in staff offices'. Since the proposed study poses no greater than minimal risk to participants, a DSMB is not necessary. The Primary Investigator and Co-Investigators will be responsible for ensuring data integrity and safety monitoring of human subjects who are involved in the research, along with the Data Safety officer.

20.2 Describe what data are reviewed, including safety data, untoward events, and efficacy data.

Response:

Study questionnaires, experimental sessions, measurements, and videotape data that are collected by study personnel will be monitored.

20.3 Describe any safety endpoints.

Response:

Since this study does not involve more than minimal risk, there are no primary or secondary safety endpoints.

20.4 Describe how the safety information will be collected (e.g., with case report forms, at study visits, by telephone calls with participants).

Response:

Safety information will be collected by the project coordinator and reported to both the UBIRB and the Safety Officer in the time frames outlined by the UBIRB.

20.5 Describe the frequency of safety data collection.

Response:

Data, including all follow up data, will be collected through 2022 at the University at Buffalo.

20.6 Describe who will review the safety data.

Response:

The Principle Investigator and Co-Investigators will review the data.

20.7 Describe the frequency or periodicity of review of cumulative safety data.

Response:

The primary investigator will be responsible for monitoring data safety at the weekly meetings with study personnel.

20.8 Describe the statistical tests for analyzing the safety data to determine whether harm is occurring.

Response:

This study poses less than minimal risk; therefore, there are no stopping criteria

20.9 Describe any conditions that trigger an immediate suspension of the research.

Response:

This study poses less than minimal risk; therefore, there are no stopping criteria

21.0 Withdrawal of Subjects

N/A: This study is not enrolling subjects. This section does not apply.

21.1 Describe anticipated circumstances under which subjects may be withdrawn from the research without their consent.

Response:

Subjects may be withdrawn from the research if they fail to follow study procedures (i.e. failure to follow study related directions). With some reason, if the infant's discomfort (i.e.: fuss and cry) persisted throughout the procedure, the parent will be given permission to stop their infant from continuing the study.

21.2 Describe any procedures for orderly termination.

NOTE: Examples may include return of study drug, exit interview with clinician. Include whether additional follow up is recommended for safety reasons for physical or emotional health.

Response:

Participants will be debriefed about the nature of the study and the reason for their removal.

21.3 Describe procedures that will be followed when subjects withdraw from the research, including retention of already collected data, and partial withdrawal from procedures with continued data collection, as applicable.

Response:

Participants can withdraw from the research at any time. If participants withdraw no further data will be collected, but any information that had been provided may be retained by the researcher and analyzed.

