Once the child turns 2-4 years of age, families, regardless of if they were randomized to the intervention classes, will be invited back to complete additional tasks. These tasks include games that measure impulsivity and effortful control. Along with these games, parents will be asked to complete additional questionnaires: the temperament questionnaire, early childhood behavior questionnaire, and children's behavior questionnaire. The child will complete the food reinforcement game again, height and weight will be collected, and skinfold thickness will be measured.

If for any reason the participant is unable to attend an assessment period at the South Campus, we will plan to visit them at their home in order to obtain the child's height/weight. They will be provided \$15 compensation for this visit.

If for any reason they are unable to attend the assessment period at the South Campus and we are unable to come to their home, we will contact their child's Pediatrician office to learn the child's most recent height/weight for that time period.

10.2 Describe what data will be collected.

NOTE: For studies with multiple data collection points or long-term follow up, consider the addition of a schedule or table in your response.

Response:

Item	Months						
	0	3	6	12	24	2-4y	
Demographic and socioeconomic variables	X						
Pregnancy History and Feeding Practices Questionnaire	X						
Baby Eating Behavior Questionnaire (BEBQ)	X						
Infant Daily Health Survey	X	X	X	X	X	X	
Infant Behavior Questionnaire- Revised (IBQ-R)	X						
Infant food/non-food reinforcement task	X	X	X	X	X	X	
Infant Diet and energy intake	X	X	X	X	X	X	
Infant and Parental anthropometrics	X	X	X	X	X	X	

Infant Toddler-Home Observational Measurement of Environment (IT-HOME) (During COVID-19 social distancing, this will be virtual)	X		X	X	X	
Parental Reinforcing Value of Food and Activities Questionnaire	X	X	X	X	X	X
Block Food Frequency Questionnaire	X	X	X	X	X	X
Child Health and Medical Care Questionnaire				X	X	X
Skinfold Thickness Measurement						X
Effortful control tasks						X
Temperament Questionnaires						X
Music/Play surveys (during COVID-19 social distancing) as needed at whatever assessment groups are in				X	X	X
Perceived stress scale (during COVID-19 social distancing) as needed at whatever assessment groups are in				X	X	X

a) Anthropometric data

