18.0 Data Management and Analysis

18.1 *Describe the data analysis plan, including any statistical procedures. This section applies to both quantitative and qualitative analysis.*

Response:

Descriptive statistics will be determined, and the distribution of each variable will be examined to assess normality. Appropriate transformations based on the distribution will be considered prior to analysis. Mixed model analysis of covariance (ANCOVA) will be used to examine the changes in the motivation to eat versus motivation to engage in alternative behaviors (FRR), infant daily energy intake, zWFL and home environment between the music and control groups. All analyses will be intention to treat, and will include all families that are randomized. The primary outcomes will be analyzed using SAS PROC MIXED (mixed ANCOVA), which will include random intercepts and time effects clustered within participants, adjusting for any family, parental, and infant temperament confounders that are different between the groups. Mixed ANCOVA accounts for repeated observations over time of participants,

and allows analysis with missing data. The models examine group (music or control), time in months (0, 3, 6, etc.) and their interaction as class variables and planned comparisons will be done assessing group differences to specific measurement interval after randomization (3, 6, 12, and 24 months). FRR, daily energy intake, zWFL, and home environment enrichment score are expected to be different between groups from baseline through the 2-year study. We predict that the relative reinforcing value of music will increase as the program is extended from 6 weeks to one year, and the reinforcing value of food will decrease during the year of intervention. Since the intervention is designed to enrich the home environment to support greater involvement in music, we expect the increased reinforcing value of music and the decreased reinforcing value of food to be maintained during maintenance period. In addition, we predict infants in the music group will show less weight for length gain over time compared to the control group at 12 and 24-month assessments. All analysis will be computed using SYSTAT and SAS .

18.2 If applicable, provide a power analysis.

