NOTE: This may not apply to certain types of studies, including chart/records reviews, survey studies, or observational studies. This question is asked to elicit whether the investigator has an adequate sample size to achieve the study objectives and justify a conclusion.

Response:

The sample size for this proposal is based on the effect size of our pilot randomized controlled trial of an enriched music experience versus play dates on reducing relative food reinforcement and standardized weight for length in 9-15-month-old infants who were high in food reinforcement. Between groups differences in FRR showed an effect size (ESd) of 0.978. To detect differences for an ESd = 0.978 between the music and control groups with power at 0.80 and alpha at 0.05, 18 subjects per group are needed. The effects for standardized weight for length showed an ESd of 0.712 in zWFL differences between groups. Differences this large with power at 0.80 and alpha at 0.05 can be observed with 32 subjects per group. To be conservative, we will use a lower ESd = 0.667 for differences in infant weight (zWFL) change between groups. At power at 0.8 and alpha at 0.05, 37 subjects per group are needed. To control for attrition, we will recruit an additional 25% of parent-infant dyads at baseline, which will bring our total amount to be 46 subjects per group, or 92 subjects total. We feel as if this is a conservative estimate of treatment effects since this is a smaller effect size than we observed at six weeks in the pilot study, and we realistically think that the effects will be greater after a year of intervention.

18.3 Describe any procedures that will be used for quality control of collected data.

Response:

The primary investigator will be responsible for monitoring data safety at the weekly meetings. This includes ensuring confidentiality procedures are being followed in both recruitment and data collection. The types of data that will be monitored include demographic information and responses to questionnaires and assessments. The primary investigator will also be responsible for reporting serious events that occur during the laboratory sessions to the SBSIRB within 48 hours. The only anticipated serious event would be an allergic reaction to a food, previously unknown to the participant

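### Sections 21.1 and 21.3 do not separate stopping classes from leaving the research, so later outcomes of randomised families may go uncollected

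*Combined protocol and SAP*

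**What the plan says.** Section 21.1 answers a prompt about withdrawal without the subject's consent: "Subjects may be withdrawn from the research if they fail to follow study procedures". The only gloss is a reference to study-related directions. Classes, home practice and assessments are not told apart.

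Section 21.3 states "If participants withdraw no further data will be collected", and that information already given may be kept and analysed. Its prompt asks about "partial withdrawal from procedures with continued data collection, as applicable". The response does not take this up.

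Section 18.1 promises "All analyses will be intention to treat, and will include all families that are randomized". The model is a mixed ANCOVA "which will include random intercepts and time effects clustered within participants", with planned group comparisons at 3, 6, 12 and 24 months. It is said to allow for missing data. No missing-data assumption or sensitivity analysis is named.

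Section 10.1 has two provisions for assessment outside the usual visits. A home visit, and failing that the pediatrician's record, supplies height and weight "If for any reason the participant is unable to attend an assessment period at the South Campus". At 2-4 years, families "regardless of if they were randomized to the intervention classes, will be invited back to complete additional tasks".

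Section 18.2 covers losses by numbers: "To control for attrition, we will recruit an additional 25% of parent-infant dyads at baseline".

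**The concern.** A family can stop attending classes and still be assessed. For an intention-to-treat comparison these are different events, and the plan has no category for the first. The programme asks for 37 weekly sessions and then monthly ones, with home practice alongside, so some families can be expected to fall away.

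If staff treat that as failing to follow study directions, the family leaves the research and its later outcomes are never measured. The reason for the loss would then be adherence, which may be related to outcome. The 12- and 24-month contrasts could come to rest more on families who follow directions than on all families randomised. Because the rule is discretionary, it could also be applied differently from one family, or one arm, to another.

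**Working it through.** **1. Does removal reach classes?** Two features point towards it: classes and home practice are described in Section 10 under its heading for study procedures, and 21.1 removes subjects from the research as a whole. Others point away: the next sentence of 21.1 concerns a distressed infant, which fits a laboratory task; 10.1 only encourages home practice; and makeup sessions are offered. No section makes attendance a condition of staying in. The question is open.

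**2. Does the data stop apply to team removals?** The sentence in 21.3 is written for participants who withdraw. No other rule covers families whom the team removes. Applying it to them is the natural reading, but an inference.

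**3. What would be lost, and what could replace it?** The 10.2 schedule has the reinforcement task, infant diet and anthropometrics at 3, 6, 12 and 24 months, and IT-HOME at 6, 12 and 24.

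| Route | Supplies | Stated to cover removed families? |
|---|---|---|
| Home visit or pediatrician (10.1) | Height and weight only | No; families unable to attend |
| 2-4-year visit (10.1, 10.2) | Reinforcement task, diet, anthropometrics; no IT-HOME | No; invites families whether or not randomised |

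Infants enter at 9-15 months, so month 24 falls at 9 + 24 = 33 to 15 + 24 = 39 months of age, inside the 24-48-month window. The 2-4-year visit could therefore give FRR, diet and anthropometrics near month 24. It is not a planned comparison time in 18.1.

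**4. What does the model recover?** Let f be the share of an arm that is removed, S the stayers, R the removed, and obs the visits before removal. With known covariance, the error in that arm's month-24 mean is

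f × { [μ_S(24) − μ_R(24)] + B × [μ_R(obs) − μ_S(obs)] }, with B = Cov(24, obs) × Var(obs)⁻¹.

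The error is zero when the gap at month 24 is exactly what the earlier gap predicts, as it is under missing at random. The error in the treatment effect is the difference between the two arms' errors, so equal errors cancel. The documents give no f, no outcome gap and no variance components. The sign is open too. With random time effects, a gap that widened before removal is projected to keep widening; if it in fact levels off, the model over-corrects. With intercepts only, it may under-correct. No figure for the bias can be derived.

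**5. Does the attrition allowance help?** Reproducing 18.2: a two-sample t-test with effect size 0.667, alpha 0.05 two-sided (sidedness is not stated, but two-sided matches) and power 0.80 needs 36.27, rounded up to 37 per group, as stated. Then 37 × 1.25 = 46.25, stated as 46. The allowance is 46 − 37 = 9 per arm, or 9/46 = 19.6%, for all causes. Losing 9 leaves 37 and power of 0.81. This protects power. It does not address which families are lost.

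**The case against.** The case against is a fair one. Harm needs a chain of conditions: classes must count as study procedures, a discretionary rule must be used on randomised families, 21.3 must apply to them, the data must not be missing at random, and the resulting errors must differ between arms. The text around 21.1 fits laboratory conduct better than attendance. Section 26.0 pays per completed laboratory visit and dietary recall, not per class, although a bonus rewards completing the entire study. Section 27.4 has families contacted yearly about appointments. Survey completion in the pilot was nearly equal (85.4% music, 84.8% play date). Nothing says that a family that stops classes has withdrawn, and fuller wording may exist in the consent form or in the procedures manuals mentioned in 14.4, neither of which is available here.

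All of this stands as a limit on the strength of the point. It does not close the gap: none of it tells staff what to do when a randomised family stops attending, and none of it keeps such a family in the planned assessments.

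A reader might go further and infer that the plan contradicts its own intention-to-treat promise. It does not: data collected before removal are kept, and the mixed model uses them. A reader might also infer that missing classes leads to removal. No section says so.

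**Conclusion.** The point holds as a gap in the follow-up rules that is worth closing, with medium confidence. As written, 21.1 and 21.3 can be used on randomised families in a way that ends measurement of FRR, zWFL, home environment and diet, and 18.1 then relies on missing at random without saying so. This rests on two readings that the text permits but does not settle: that classes or home practice fall under study procedures, and that 21.3 governs removals by the team.

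No magnitude should be attached. A reader might infer that the music effect would be overstated, or try to size the bias from the 19.6% allowance. The documents do not support either: they give no removal rate, no outcomes for removed families and no covariance, and the sign itself depends on those inputs. The existing fallbacks and the 2-4-year visit may limit the loss. None of them is stated to cover removed families, and together they do not supply all the outcomes at the planned times.

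**What to change.** - **Section 21.1:** state that non-adherence to classes or home practice does not by itself end a randomised family's follow-up.
- **Section 21.3:** separate stopping classes from leaving the research. Keep inviting families who stop to the existing 3-, 6-, 12- and 24-month assessments. Extend the 10.1 home-visit and pediatrician height/weight routes to them where parents permit. Reserve the end of data collection for parents who withdraw permission for it.
- **Records:** log the arm, date and reason of each removal, so that readers can judge whether losses were balanced.

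The cost is protocol wording and possibly consent wording, plus some extra effort to contact families who no longer attend. Section 10.4, which says that no source records are used, would need to be aligned with the pediatrician route. The assessments and both fallbacks already exist.

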22.0 Risks to Subjects

22.1 List the reasonably foreseeable risks, discomforts, hazards, or inconveniences to the subjects related to their participation in the research. Consider physical, psychological, social, legal, and economic risks. Include

a description of the probability, magnitude, duration, and reversibility of the risks.

NOTE: Breach of confidentiality is always a risk for identifiable subject data.

Response:

There are no greater than minimal physical, psychological, social or legal risks associated with participating in the study. Caregivers may feel uncomfortable answering some of the demographic, infant feeding and behavior questions. Additionally, the infant may experience some anxiety when entering a new environment- the laboratory and/or interacting with new people- the experimenters; however, we are hoping that this feeling will be temporary. A breach of confidentiality is also possible, although unlikely, due to the identifiable subject data.

22.2 Describe procedures performed to lessen the probability or magnitude of risks, including procedures being performed to monitor subjects for safety.

Response:

Caregiver's discomfort toward questionnaires will be minimized by telling participants that they do not have to answer any questions that they are uncomfortable with, and that all responses will be kept strictly confidential.

22.3 If applicable, indicate which procedures may have risks to the subjects that are currently unforeseeable.

Response:

The food reinforcement task may have unforeseeable risks if the infant has an unknown food allergy.

22.4 If applicable, indicate which research procedures may have risks to an embryo or fetus should the subject be or become pregnant.

Response:

N/A

22.5 If applicable, describe risks to others who are not subjects.

Response:

N/A

23.0 Potential Benefits to Subjects

23.1 Describe the potential benefits that individual subjects may experience by taking part in the research. Include the probability, magnitude, and duration of the potential benefits. Indicate if there is no direct benefit.

*NOTE: Compensation **cannot** be stated as a benefit.*

Response:

There are no potential benefits to individual subjects.

